3.7.3. Selection of Data in the Event of Multiple Records in a Window

Depending on the statistical analysis method, single values are required for each analysis window. For example, change from baseline by visit usually requires a single value, whereas a time-to-event analysis would not require 1 value per analysis window. When a single value is needed, the following rule(s) will be used.

For baseline, the last available record on or prior to the first dose of study drug will be selected. For DXA BMD, it is defined as the last value on or prior to Study Day 14. If there are multiple records with the same time or no time recorded on the same day for numeric observations, average will be computed for that day, except that for HBV DNA and Quantitative HBsAg, geometric mean will be taken. If there are multiple records with the same time or no time recorded on the same day for categorical observations, the most conservative value will be taken, eg, negative will be selected over positive for HBeAg and HBsAg, and positive will be selected over negative for HBeAb and HBsAb.

The following specified rules will be used for postbaseline visits:

- **ALT:** The largest value will be included in the analysis when 2 or more ALT values occur within the same visit window.
- **BMD:** The latest record in the window will be selected.
- **HBV DNA (IU/mL) and Quantitative HBsAg (IU/mL):** The record closest to the nominal day for that visit will be selected. If there are 2 records equidistant from the nominal day, the latest will be selected. If there is more than 1 record on the selected day, the geometric mean will be taken.
- **Serology:** For HBeAg, HBeAb, HBsAg, and HBsAb, the record closest to the nominal day for that visit will be selected. If there are 2 records equidistant from the nominal day, the latest will be selected. If there is more than 1 record on the selected day, the most conservative value will be taken, ie, positive will be selected over negative for HBeAg and HBsAg, and negative will be selected over positive for HBeAb and HBsAb.

For all other laboratory parameters:

- If multiple valid non-missing **numeric** observations exist in a window, then records will be chosen as follows:
 - The record closest to the nominal day for that visit will be selected. If there are 2 records equidistant from the nominal day, the latest will be selected. If there is more than 1 record on the selected day, the average will be taken.
- If multiple valid non-missing **categorical** observations (eg, safety ECG results) exist in a window, then records will be chosen as follows:
 - The most conservative value (eg, abnormal will be selected over normal for safety ECG) within the window will be selected. In the event that 2 values within a window are of equal abnormality, the value collected nearest to the nominal date will be used.

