- Blood sample for serum chemistry and liver function tests, hematology, plasma HBV DNA, serum HBsAg (quantitative), HBV serology (HBsAg and reflex HBsAb), plasma PK, virology (resistance surveillance), and serum and plasma for storage
- Estimated creatinine clearance (using the Cockcroft-Gault method)
- Urine sample for urinalysis, pregnancy test (for females of child-bearing potential; in case of a positive urine test, a serum pregnancy test will be done), and for storage
- Ophthalmologic assessment, including fundoscopic examination with slit lamp and retinal photographs (both eyes) (**substudy subjects only at select sites** - separate consent required)

6.3.1.6. Week 36

- Symptom directed physical exam
- Body weight
- Vital signs: blood pressure, pulse, respiration rate, and temperature
- Review concomitant medications
- Review adverse events
- Perform study drug accountability
- Dispense blinded study drugs
- Blood sample for serum chemistry and liver function tests, hematology, plasma HBV DNA, serum HBsAg (quantitative), HBV serology (HBsAg and reflex HBsAb), plasma PK, virology (resistance surveillance), and serum and plasma for storage
- Estimated creatinine clearance (using the Cockcroft-Gault method)
- Urine sample for urinalysis, pregnancy test (for females of child-bearing potential; in case of a positive urine test, a serum pregnancy test will be done), and for storage

6.3.1.7. Week 48

- Complete physical exam including, vital signs (blood pressure, pulse, respiration rate and temperature), and body weight
- ECG (subjects must rest quietly in the supine position for a minimum of 5 minutes prior to the recording)
- DXA scan of spine and hip (within –14 days of the expected visit date; at sites in China with capability only)
- Review concomitant medications
- Review adverse events
- Perform study drug accountability
- Fasting blood sample for bone biomarkers and metabolic assessment (glucose and lipid panel [total cholesterol, HDL, direct LDL, and triglycerides]) - no food or drinks, except water, at least 8 hours prior to blood collection
- Fasting urine sample for renal biomarkers
- Dispense blinded study drugs
- Blood sample for serum chemistry and liver function tests, hematology, plasma HBV DNA, serum HBsAg (quantitative), HBV serology (HBsAg and reflex HBsAb), plasma PK, virology (resistance surveillance), and serum and plasma for storage
- Estimated creatinine clearance (using the Cockcroft-Gault method)

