7.5.4. Management of Bone Evaluation

As there is uncertainty surrounding the clinical significance and management of decreases in bone mineral density for chronic HBV- infected patients, Gilead recommends that any subject who has a DXA scan that demonstrates a decrease from baseline of > 5% in bone mineral density of the spine region or the hip region be followed per local medical practice at the discretion of the investigator.

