8.1.3. Secondary Endpoints

The key secondary safety endpoints are:

- The percent change from baseline at Week 48 in hip BMD
- The percent change from baseline at Week 48 in spine BMD
- The change from baseline at Week 48 in serum creatinine

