Fasting Urine for Renal Biomarkers ⁱ		X		X		X		X		X	
Fasting Metabolic Panel ^j		X		X		X		X		X	
Urine Pregnancy Test ^k	X	X	X	X	X	X	X	X	X	X	X

Visit windows	Week										
	168	192	216	240	264	288	312	336	360	384/ED ^o	FU ^p
	±28 days										
Urinalysis	X	X	X	X	X	X	X	X	X	X	X
Serum and plasma for storage	X	X	X	X	X	X	X	X	X	X	X (serum only)
Urine for Storage	X	X	X	X	X	X	X	X	X	X	
Ophthalmologic substudy ⁿ – fundoscopic examination with slit lamp										X ⁿ	
Hepatic Ultrasound ^f	X	X	X	X	X	X	X	X	X	X	

- a The visit window for Week 48 visit is –14 days. The visit window for Week 96 is ±14 days.
- b Subjects must rest quietly in the supine position for a minimum of 5 minutes prior to the recording
- c Vital signs include blood pressure, pulse, respiration rate, and temperature
- d DXA scans will be performed only at sites in China with capability. The initial (baseline) DXA will be performed during Screening and should be completed at least 14 days prior to the first dose of study drug. The Week 48 DXA window is –14 days only. DXA is required for Early Discontinuation (ED) visit if not done within the last 24 weeks. Subjects already assigned to open-label TAF 25 mg QD per Amend 2.1 continue on open-label TAF 25 mg QD. Otherwise, blinded study drug will be dispensed until Week 144 visit. Open label TAF will be dispensed from Week 144 through Week 360. At Week 384/ED, study drug will not be dispensed
- f It is preferred that subjects take their study drug according to a morning dosing schedule; subjects who elect to dose in the evening the previous day are not required to have in-clinic dosing and provide the single PK sample being collected at Week 4 and 12 visits.
- g Serum chemistry and Liver Function Tests : alkaline phosphatase, AST, ALT, GGT, total bilirubin, direct and indirect bilirubin, total protein, albumin, LDH, CPK, bicarbonate, BUN, calcium, chloride, creatinine, glucose, phosphorus, magnesium, potassium, sodium, uric acid, and amylase (reflex lipase testing is performed in subjects with total amylase > 1.5 × ULN), and PTH. PTH analyzed at all visits except for Screening through Week 96, and then at Weeks 120, 144, and then every 48 weeks through Week 384/ED. At Baseline, Weeks 24, 48, 72, 96, 120, 144, 192, 240, 288, 336 and 384/ED, subject will be fasting for serum and glucose and metabolic panel. Coagulation panel will be done at Screening and then as a reflex only test for ALT flares.

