3.7.2. Analysis Windows

Subject visits might not occur on protocol specified days. Therefore, for the purpose of analysis, observations will be assigned to analysis windows.

The following windows (Table 3-2 to Table 3-8) apply to baseline and on-treatment assessments only, ie, data collected up to the last dose date for those who discontinued study drug prematurely (except efficacy data [HBV DNA, quantitative HBsAg, HBV serology, ALT, fibrotest score] for subjects who discontinue study drug after Week 48 due to HBsAg loss with confirmed seroconversion to anti-HBs), or data collected up to database finalization date for those who have not discontinued study drug permanently.

For subjects who discontinue study drug early due to HBsAg loss with confirmed seroconversion, all efficacy data including data collected after the last dose date of the study drug will be reassigned analysis visits using the on-treatment assessment windows (Table 3-2, Table 3-3, and Table 3-5).

The analysis windows for HBV DNA, hematology, serum chemistry and liver function tests, urinalysis, urine pregnancy test, eGFR (by CG and Chronic Kidney Disease Epidemiology Collaboration [CKD-EPI]), renal biomarkers urine albumin to creatinine ratio (UACR), urine protein to creatinine ratio (UPCR), renal tubular maximum reabsorption rate of phosphate to the glomerular filtration rate (TmP/GFR), urine fractional excretion of filtered phosphate (FEPO₄), fractional excretion of uric acid (FEUA), weight, and vital sign assessments are presented in Table 3-2.

Table 3-2. Analysis Windows for HBV DNA, Hematology, Serum Chemistry and Liver Function Tests, Urinalysis, Urine Pregnancy Test, eGFR (by CG and CKD-EPI), PTH, UACR, UPCR, TmP/GFR, FEPO₄, FEUA, Weight, and Vital Sign Assessments

Visit ID	Nominal Day	Lower Limit	Upper Limit
Baseline			1
Week 4	28	2	41
Week 8	56	42	69
Week 12	84	70	97
Week 16	112	98	125
Week 20	140	126	153
Week 24	168	154	181
Week 28	196	182	209
Week 32	224	210	237
Week 36	252	238	265
Week 40	280	266	293
Week 44	308	294	321
Week 48	336	322	363
Week 56	392	364	419
Week 64	448	420	475
Week 72	504	476	531
Week 80	560	532	587
Week 88	616	588	643
Week 96	672	644	713
Week 108	756	714	797
Week 120	840	798	881
Week 132	924	882	965
Week 144	1008	966	1091
Week 168	1176	1092	1259
Week 192	1344	1260	1427
Week 216	1512	1428	1595
Week 240	1680	1596	1763
Week 264	1848	1764	1931
Week 288	2016	1932	2099
Week 312	2184	2100	2267
Week 336	2352	2268	2435
Week 360	2520	2436	2603

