Week 384	2688	2604	2771

The analysis windows for safety ECG and fibrotest are presented in Table 3-3.

Table 3-3. Analysis Windows for Safety ECG and Fibrotest

Visit ID	Nominal Day	Lower Limit	Upper Limit
Baseline			1
Week 48	336	2	503
Week 96	672	504	839
Week 144	1008	840	1175
Week 192	1344	1176	1511
Week 240	1680	1512	1847
Week 288	2016	1848	2183
Week 336	2352	2184	2519
Week 384	2688	2520	2855

The analysis windows for BMD results from DXA, and fasting lipid panel including direct low density lipoprotein (LDL), high density lipoprotein (HDL) and total cholesterol to HDL ratio, are presented in Table 3-4.

Table 3-4. Analysis Windows for BMD Results from DXA and Fasting Lipid Panel

Visit ID	Nominal Day	Lower Limit	Upper Limit
Baseline			1(14 ^a)
Week 24	168	2(15a)	251
Week 48	336	252	419
Week 72	504	420	587
Week 96	672	588	839 (755 ^b)
Week 120 ^b	840	756b	923b
Week 144	1008	840 (924 ^b)	1175
Week 192	1344	1176	1511
Week 240	1680	1512	1847
Week 288	2016	1848	2183
Week 336	2352	2184	2519
Week 384	2688	2520	2855

a This applies to DXA only. Upper limit for baseline DXA BMD is Day 14 and lower limit for Week 24 DXA BMD is Day 15.

b This applies to the subjects who consented to Amendment 3.1.

The analysis windows for serum HBsAg (quantitative) and HBV serology are presented in Table 3-5.

Table 3-5. Analysis Windows for Serum HBsAg (Quantitative) and HBV Serology

Visit ID	Nominal Day	Lower Limit	Upper Limit
Baseline			1
Week 12	84	2	125
Week 24	168	126	209
Week 36	252	210	293
Week 48	336	294	391
Week 64	448	392	503
Week 80	560	504	615
Week 96	672	616	713
Week 108	756	714	797
Week 120	840	798	881
Week 132	924	882	965
Week 144	1008	966	1091
Week 168	1176	1092	1259
Week 192	1344	1260	1427
Week 216	1512	1428	1595
Week 240	1680	1596	1763
Week 264	1848	1764	1931
Week 288	2016	1932	2099
Week 312	2184	2100	2267
Week 336	2352	2268	2435
Week 360	2520	2436	2603
Week 384	2688	2604	2771

The analysis windows for fasting glucose, fasting total cholesterol, fasting triglycerides, renal biomarkers including urine retinol binding protein (RBP) to creatinine ratio, urine beta-2-microglobulin to creatinine ratio, and bone biomarkers including C-type collagen sequence (CTX), procollagen type 1 N-terminal propeptide (P1NP), osteocalcin (OC), and bone specific alkaline phosphatase (bsAP) are presented in Table 3-6.

Table 3-6. Analysis Windows for Fasting Glucose, Fasting Total Cholesterol, Fasting Triglycerides, Renal, and Bone Biomarkers

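### The SAP's latest-record rule for BMD lets an unscheduled scan as late as Day 419 replace a valid on-time Week 48 scan

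*SAP*

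**What the plan says.** Percent change in hip and spine BMD at Week 48 are key secondary safety endpoints (Protocol 8.1.3: "The percent change from baseline at Week 48 in hip BMD", with the matching line for spine).

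The protocol times the scan tightly. The Week 48 visit text in Protocol 6.3 reads "DXA scan of spine and hip (within –14 days of the expected visit date; at sites in China with capability only", and footnote d of Appendix 2 adds "The Week 48 DXA window is –14 days only".

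The SAP assigns scans to visits more widely. The Table 3-4 row for BMD is "Week 48 336 252 419" (nominal day, lower limit, upper limit). When several BMD records fall in that window, SAP 3.7.3 states "The latest record in the window will be selected".

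HBV DNA, quantitative HBsAg, serology and the default numeric laboratory parameters follow a different rule: "The record closest to the nominal day for that visit will be selected". That default covers serum creatinine, the third key secondary endpoint in the protocol, whose window in Table 3-2 is "Week 48 336 322 363". ALT takes the largest value.

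The SAP gives no reason for the BMD rule. It does not limit the rule to technically failed scans, and it states no preference for a scan inside the protocol window.

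**The concern.** The upper limit of Day 419 lies almost 12 weeks after the target day. Combined with the latest-record rule, this means that a valid on-time scan is discarded whenever a later one exists in the window, and a value from about Week 60 is labelled Week 48. The same selected record feeds the mean percent change and the table that counts subjects with losses above 5% and above 7% (SAP 7.3.1).

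What is at stake is whether the reported value is a Week 48 value when a valid one is in hand. There is also a possible selection effect if extra scans depend on the first result.

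**Working it through.** **1. The SAP window reproduces.** Scheduled DXA days are 168, 336 and 504 (Weeks 24, 48, 72). The midpoints give (168 + 336)/2 = 252 and (336 + 504)/2 − 1 = 419, as in Table 3-4. The upper limit is 419 − 336 = 83 days past target (11.9 weeks). The protocol window is Days 336 − 14 = 322 to 336.

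**2. Which scans can trigger the override?**
- Week 24 scan (±14 days): Days 154-182. Outside the window.
- Week 72 scan (±14 days): Days 490-518. Outside the window.
- Early-discontinuation scan: required only if none was done in the previous 24 weeks, so after an on-time Week 48 scan not before 322 + 168 = Day 490. Outside the window.

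Only an unscheduled or repeat scan on Days 337-419 displaces an on-time scan.

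**3. Drift alone.** Assume that BMD change is linear in time at the planning means (Protocol 8.8: spine −1.69% TDF, −0.69% TAF; hip −1.17%, −0.17%). If every value came from Day 419, the 1.00-point difference would become 419/336 = 1.25. If a fraction q of subjects had such a scan, regardless of result, the difference would widen by at most q × 83/336:

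| q (assumed) | widening, points |
|---|---|
| 2% | 0.005 |
| 5% | 0.012 |
| 10% | 0.025 |
| 20% | 0.049 |

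**4. Repeats prompted by a low reading.** Suppose instead that a fraction p of subjects with a first reading below −5% are rescanned, and that a fraction f of the change variance is measurement error, split equally between the baseline and follow-up scans. Neither p nor f is in the documents; take p = 0.25 to 1 and f = 0.25 to 0.50.

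With z = (−5 − mean)/SD and the planning SDs (3.08% spine, 2.20% hip):

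| | z, TDF | z, TAF | P(< −5%), TDF | P(< −5%), TAF | SD·φ(z), TDF | SD·φ(z), TAF |
|---|---|---|---|---|---|---|
| Spine | −1.075 | −1.399 | 14.1% | 8.1% | 0.690 | 0.462 |
| Hip | −1.741 | −2.195 | 4.1% | 1.4% | 0.193 | 0.079 |

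Regression to the mean raises an arm's mean by p × (f/2) × SD·φ(z). The TAF-TDF difference therefore shrinks by p × (f/2) × 0.228 at spine and p × (f/2) × 0.114 at hip. Linear drift to Day 415 lowers an arm's mean by p × P(< −5%) × |mean| × (415/336 − 1 = 0.235), which widens the difference by p × 0.043 at spine and p × 0.011 at hip.

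| p, f | Spine, no drift | Spine, drift to Day 415 | Hip, no drift | Hip, drift to Day 415 |
|---|---|---|---|---|
| 0.25, 0.25 | 0.993 | 1.004 | 0.996 | 0.999 |
| 0.25, 0.50 | 0.986 | 0.996 | 0.993 | 0.996 |
| 1, 0.25 | 0.971 | 1.014 | 0.986 | 0.996 |
| 1, 0.50 | 0.943 | 0.986 | 0.971 | 0.982 |

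At spine the sign changes with f and with the timing of the rescan. The no-drift columns are the limit for a rescan soon after Day 336.

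**5. Against the precision available.** If all 150 China subjects (100:50) had DXA, the SE of the spine difference would be 3.08 × √(1/100 + 1/50) = 0.53 points. The largest shift in step 4, 0.057, is about 0.11 SE. Since DXA is done only at capable sites, the actual SE will be larger.

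**6. Under a closest-day rule.** An on-time scan is at most 14 days from Day 336, so a later scan can displace it only up to Day 350. A Day 336 scan is never displaced.

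**The case against.** - **A visit window and an analysis window do different jobs.** One governs site conduct, the other assigns records. Midpoint limits are ordinary, and SAP 3.7.2 explains that visits may fall off schedule. This stands: the difference in width between the two documents is not a fault.
- **The rule may be deliberate.** A repeat after a poor scan should replace it, ALT also has its own rule, and the BMD baseline likewise takes the last value. This is plausible, but the SAP does not say so, and the rule as written also discards valid scans.
- **It may never operate.** This stands: no scheduled scan triggers it.
- **A reader might infer that repeats follow low readings and so shrink the TAF-TDF difference.** Protocol 7.5.4 recommends that subjects with a loss above 5% "be followed per local medical practice at the discretion of the investigator". It mentions no repeat DXA, no timing and no entry of a local scan into the study data. Step 4 shows that the sign is not fixed even if such repeats are assumed.
- **Late scans are still on blinded randomized treatment,** since SAP 1.2 keeps China subjects double-blind for three years. This stands: there is no treatment contamination.
- **The data will be visible.** Listings 42.1 to 43.2 give the BMD results and the subjects with more than a 5% decline. That allows a check afterwards but does not correct the summaries.

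**Conclusion.** The point holds in a limited form. As written, SAP 3.7.3 reports a later unscheduled scan, up to Day 419, as the Week 48 BMD value even when a valid scan from Days 322-336 exists, and nothing in either document prevents this.

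The number of subjects affected is unknown and may be zero. Any shift in the mean difference is likely to be a few hundredths of a point, with unknown sign. That size rests on assumed rescan rates, error variance and linear bone loss, and on planning means and SDs set for the non-China sample.

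This SAP covers the China subjects only and summarizes BMD descriptively, so no test, alpha or power figure is affected. The documents do not support reading this as a bias toward no difference, or as a conflict created by the wider window alone. It is an inexpensive improvement.

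**What to change.** In SAP 3.7.3, replace the BMD rule: select the valid record closest to the nominal day, taking the latest if two are equidistant, as for HBV DNA and the default numeric laboratory parameters. Allow a later repeat to replace it only when the earlier scan was recorded as technically unacceptable. Leave the Table 3-4 window unchanged, so that a late scan still counts when no on-time scan exists.

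If the latest-record rule is kept, state the reason and add a closest-scan sensitivity summary.

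The cost is one sentence in the SAP and one sort rule in programming, with no new data.

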4. SUBJECT DISPOSITION

4.1. Subject Enrollment

The number and percentage of subjects randomized each investigator will be summarized by treatment group and overall using the Safety Analysis Set. Similarly, the number and percentage of subjects enrolled in each randomization stratum will be summarized based on interactive voice response system/web response system (IVRS/IWRS) data.

If there are discrepancies between IVRS/IWRS and laboratory data with regard to stratum assignment, a listing of the discrepancies will be provided. If there are differences between randomization stratum for HBV DNA using screening and baseline HBV DNA value, a listing of the differences will be provided.

4.2. Disposition of Subjects

The summary of subject disposition will be provided by treatment group and overall. This summary will include the number of subjects screened, screen failure subjects who were not randomized, subjects who met all eligibility criteria and were not randomized, subjects in the Randomized Analysis Set, subjects randomized but not treated, subjects in the Safety Analysis Set, and subjects in FAS.

In addition, the number and percentage of the subjects in the following categories will be summarized using the Safety Analysis Set:

Study Drug Completion

- Remaining on double-blind study treatment up to the data-cut date
- Prematurely discontinued double-blind study treatment prior to the data-cut date (with summary of reasons for discontinuing treatment)
- Completed double-blind study treatment up to the data-cut date
- Entered open-label phase up to the data-cut date

Study Completion

- Entered 24-week treatment-free follow-up period up to the data-cut date
- Remaining on study up to the data-cut date
- Prematurely discontinued study prior to the data-cut date (with summary of reasons for discontinuing study)

- Started another HBV therapy up to the data-cut date
- Completed protocol-planned duration of the study up to the data-cut date

A data listing of reasons for premature study drug/study discontinuation will be provided.

4.3. Extent of Exposure

Exposure data described below will be summarized for the double-blind phase only.

4.3.1. Duration of Exposure to Blinded Study Drug

Duration of exposure to blinded study drug will be defined as (last dose date of blinded study drug – first dose date of blinded study drug + 1), regardless of temporary interruptions in study drug administration, and will be expressed in weeks (recorded to 1 decimal place, eg, 4.5 weeks). If subjects are still on blinded study drug, the latest of blinded study drug start and end dates, and the clinic and laboratory visit dates (excluding the open-label and 24-week treatment-free follow-up visit dates) will be used to impute the last dose date of blinded study drug for calculating the duration of blinded study drug exposure.

Duration of exposure to blinded study drug will be summarized using descriptive statistics (sample size, mean, standard deviation [SD], median, Q1, Q3, minimum, and maximum) and as the number and percentage of subjects exposed for specified periods, eg, ≥ 4 weeks (28 days), ≥ 8 weeks (56 days), etc.

Summaries will be provided by treatment group for subjects in the Safety Analysis Set.

Time to premature discontinuation of blinded study drug will be analyzed by the Kaplan-Meier method using the Safety Analysis Set. Subjects who completed the blinded study drug will be censored on the last dose date of blinded study drug. Subjects who remain on blinded study drug will be censored on the imputed last dose date of blinded study drug as defined in this section.

